3. ADMINISTRATIVE ORGANIZATION

This study will be conducted in the URMC Department of Psychiatry's Child and Adolescent Partial Hospital Service (CAPHS). The director of CAPHS is [name] (LCSW-R). [name] has been implementing traditional YST for a subset of patients for the last year and reports it has been both feasible and acceptable to patients, caregivers, and clinic staff in CAPHS. Administration of YST+YM will be conducted either remotely via telephone and Zoom, or a mixture of in-person (at CAPHS) and remote administration as the surrounding pandemic context and current CAPHS policy allows. *Information regarding research safety during the COVID-19 pandemic:* To ensure appropriate safety precautions when conducting in-person study procedures, the process for conducting in-person visits outlined in the Guidance for Human Subject Research (https://www.urmc.rochester.edu/coronavirus/coronavirus-research/guidance-for-researchers/human-subjects-research.aspx) will be followed. The study team will continue to monitor the guidance provided by UR/URMC for updates and revisions to

Page 3 of 64 Version Date: 12/13/21 ensure all study activities are conducted according to current safety guidelines. This protocol was constructed under consultation with [name], who provided guidance on the feasibility and acceptability of the research activities in her clinic.

4. STUDY DESIGN

This study is a two-phased, one-armed pilot trial to evaluate feasibility, acceptability, and target engagement of YST+YM. It will also facilitate estimation of clinical outcome prevalence, including suicidal ideation and attempts over the intervention period and through post-intervention follow-up.

In phase one (content refinement; n = 5-10), feasibility and acceptability will be optimized via measures of subject engagement with the intervention (i.e., text-message response rates) and with subject feedback during semi-structured interviews. We will also assess feasibility of the assessments used to measure emotion regulation, perceived social support and connectedness, and clinical outcomes (i.e., anxiety, depression, and suicidal ideation and attempts).

In phase two (pilot; n = 60-70), target engagement and prevalence of clinical outcomes will be addressed, as well as continued assessment of feasibility and acceptability of YST+YM. Consistent with specific aims above, intervention targets include engagement with treatment (i.e., initiating contact with support team members), changes in emotion regulation skills, and perceived social support and connectedness. Distal targets, including anxiety, depression, and suicidal ideation and attempts will also be assessed to establish point estimates for power analysis and sample size planning in future trials. Subject engagement with the intervention and feedback during semi-structured interviews will be used to assess feasibility and acceptability of YST+YM (following initial modification in response to phase one subject feedback).

Because the intervention lasts approximately three months per subject, the phases will be staggered, such that some subjects will be enrolled in phase two before all phase one subjects have completed their entire intervention course. For example, we anticipate that n = 5-10 phase one subjects may complete the first remote session of YST+YM within 6 weeks of the study start date. Because we collect feedback immediately following each session, this means we will have received all the information required to finalize that session's outline and content for the launch of phase two – even though these phase one subjects will have several weeks left of YST+YM overall.

This study, encompassing both phases one and two, utilizes a one-armed, within-subjects design and will run for roughly 24 total months. Youth subjects will receive the intervention (YST+YM) and will each be assessed at 4 timepoints: prior to initiating intervention (baseline, week 1), the intervention midpoint (week 6-7), the conclusion of the intervention (post-test, week 12), and then 3 months after the intervention concludes (follow-up, 24 weeks). Adult support team members will be assessed only at post-test (week 12).

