Aim 1 - To optimize YST+YM for feasibility and acceptability. Outcome: Semi-structured interviews and rating scales will identify the most and least preferred elements of the YM module. Response rates to automated text-messages will also be used to evaluate message appeal.

Aim 2 - To test target engagement: does YST+YM increase utilization of interpersonal emotionregulation strategies and social support among adolescents with recent suicidal ideation or attempts? Hypothesis: over 12 weeks of YST+YM, subjects will demonstrate increases in: (a) the number of weekly contacts initiated to supportive adults in their lives, (c) the utilization of interpersonal emotion regulation strategies, and (c) their perceived sense of social support. These gains will be maintained at 3-month post-intervention follow-up.

Aim 3: Estimate prevalence of clinical outcomes for planning of subsequent trials - what is the average rate of clinical over the course of intervention and through 3-month follow-up? Outcome: Estimates of changes in distal targets, including anxiety, depression, and suicidal ideation and attempts for the planning of larger subsequent trials.

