8. CONSENT PROCESS

Electronic documentation of consent (eConsent / eAssent): The assent / consent process informs a youth subject, their parent/legal guardian, and adult support team members about the study, indicates the participation is voluntary and he/she has the right to stop at any time. Risks are enumerated in the informed consent form and described orally during the consent process.

Page 7 of 64 Version Date: 12/13/21 The assent / consent documents are a REDCap-based electronic consent forms. The IRBapproved form is developed in REDCap, a secure, web-based, HIPAA- compliant, data collection platform with a user management system allowing project owners to grant and control varying levels of access to data collection instruments and data (e.g., read only, de-identifiedonly data views) for other users. Potential subjects participate in the assent / consent process by eConsent obtained in-person or remotely. eConsent is obtained in a private setting, prior to baseline data collection. When obtained in-person, eConsent is accessed on REDCap via the University-issued computer, tablet, or another portable electronic device. University-issued tablets are already available on the study unit and regularly available to patients. Once the eConsent form is signed and submitted, subjects will be able to receive a print out of the paper copy, download a pdf, and/or receive an email with a PDF attachment of the signed consent form. Of note, youth subjects ages 12-17 will complete an eAssent form, while youth subjects who are 18 years old will complete a subject eConsent form.

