9. STUDY PROCEDURES

Phases one and two will utilize the same study procedures. Screening will occur via consultation with youth subjects' current therapists, who have all the necessary information to confirm youth eligibility as part of their normal clinical practice. Demographic information on youths who are screened, but determined to be ineligible, will be documented; however, no identifying information will be retained on these ineligible subjects.

After screening and signing assent / consent forms, study staff collect background information from subjects, such as demographics and nomination of 3-4 trusted adults to serve as their support team, via REDCap. Parents and guardians will be involved in the nomination process and must verbally approve all of the subject's adult nominees. Then, the baseline session is scheduled. This baseline session includes both the baseline assessment and initial session of the Youth-centered Module (YM) of the YST+YM intervention. Subjects have the option of completing this visit in-person or remotely, depending on current URMC and clinic policy. Those who complete it remotely do the baseline assessment and intervention via HIPAA-compliant video conference. After the baseline session has been scheduled with the subject, study staff will contact the subject's adult support team nominees, explain the intervention to them, and then confirm they are willing and able to serve as a support team member for the subject. Per subject need/request, URMC study staff will read aloud instructions and questions to aid their responding via tablet, phone, or computer. In the case that the REDCap site is down or malfunctioning, screening, assent / consent and questionnaires are completed on paper and later entered into REDCap.

Select questionnaires from the battery are re-administered at 6 weeks (mid-intervention), 12 weeks (immediately post-intervention), and 24 weeks (follow up). All of these assessments will be completed live (via HIPAA-compliant video conference) with study staff, who will review

Page 10 of 64 Version Date: 12/13/21 subject responses for safety concerns immediately after the assessment is completed. Table 1 depicts the assessment timeline for all subjects in the study. Table 2 provides the content of all the measures included in each assessment.

Table 1. Assessment timeline by subject type

		Post- discharge week				
	Pre-discharge	1-3	4 – 6	7-10	10-12	22-24

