Adult experiences and feedback survey Format: Self-report	 Identity confirmation: Name and date of birth for longitudinal linking survey linking in database Demographics (e.g., age, race, gender) Acceptability ratings and feedback: Custom rating scales and open-ended questions about intervention 			

Recipients: Parents, adult supports Administered (2x): After first session, Weeks 10-12 Approx. duration: 15-20 mins	 acceptability, time taken, and perceived benefits for child Child depression symptoms: PROMIS Parent Proxy Short Form v2.0 - Depressive Symptoms 6a Child life satisfaction: PROMIS Parent Proxy Short Form v1.0 - Life Satisfaction 4a Adult depression symptoms: PROMIS Short Form v1.0 - Depression 4a Adult general stress: NIH Toolbox Perceived Stress Fixed Form Age 18+ v2.0
Youth social and emotional survey Format: Self-report Recipients: Youth only Administered (4x): During the three intervention sessions, follow-up (week 22-24) Approx. duration: 30-60 mins	 Identity confirmation: Name and date of birth for longitudinal linking survey linking in database Demographics (e.g., age, race, gender) Acceptability ratings and feedback: Custom rating scales and open-ended questions about intervention acceptability and perceived benefits. Depressive symptoms: PROMIS Pediatric Short Form v2.0 - Depressive Symptoms 8a Suicidal thoughts and behaviors: Short Mood and Feelings Questions about recent and historic suicide attempts Social Connectedness: Interpersonal Needs Questionnaire – Belongingness subscale Feelings of meaning and purpose: Claremont Purpose Scale – Goal-directedness and Personal Meaning subscales Emotion Regulation: Interpersonal Emotion Regulation Questionnaire - Social Modeling Subscale, Difficulties in Emotion Regulation Scale – Regulation Strategies Subscale Engagement with healthy activities: Behavioral Activation for Depression – Short form – Activation Subscale Adult support team activities: Custom questions about frequency of contact with parents and team adults on intervention support team. Questions include content about different activities (e.g., help with homework, social support) and forms of interaction (e.g., in person, over the phone).

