17. DATA ANALYSIS PLAN

For Aim 1, we will use descriptive statistics to gauge achievement of feasibility and acceptability thresholds for patients. Means above 3.5 (on a 5 point scale) will be regarded as adequate feasibility and acceptability.

For Aim 2, a linear mixed effects model will be used to evaluate (a) overall frequency of responding to text messages and (b) trends in text response rates over time. Aim 2 will also utilize generalized linear mixed effects models (fixed effect for time, with a random effect for individual) to evaluate changes in intervention target scores over time. Each of the intervention targets will serve as the outcome variable in its own separate model.

For Aim 3, means and proportions will be estimated and retained for future study planning.

A power analysis evaluating these models was conducted via simulation. For the linear mixed effects models (Aims 2), assuming a moderate effect size (d = .50) and moderate within-subject shared variance attributable (ICC = .05), simulations show this model will have adequate power (.82) to detect target engagement over the course of the intervention. Because Aims 1 and 3 utilize only descriptive statistics and require no statistical inference, no power analysis was conducted.

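### The youth ratings behind the only numerical Aim 1 mark (mean above 3.5) are not kept from the staff who deliver the sessions, so in a one-arm trial any courtesy effect goes straight into the mean

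*Combined protocol and SAP*

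**What the plan says.** Section 17 sets the only numerical criterion for Aim 1. It says "we will use descriptive statistics to gauge achievement of feasibility and acceptability thresholds for patients", and then: "Means above 3.5 (on a 5 point scale) will be regarded as adequate feasibility and acceptability". Section 2 adds "Response rates to automated text-messages will also be used to evaluate message appeal", and sections 2 and 4 also name semi-structured interviews. Neither source has a threshold.

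The only youth programme ratings listed are in section 9, Table 2, under the Youth social and emotional survey: "Custom rating scales and open-ended questions about intervention acceptability and perceived benefits". The survey's format is self-report. It carries the youth's name and date of birth for linking, and it also holds the depression and suicide items. Its timing is given as "During the three intervention sessions, follow-up (week 22-24) Approx. duration: 30-60 mins".

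On the week 6, 12 and 24 assessments, section 9 says: "All of these assessments will be completed live (via HIPAA-compliant video conference) with study staff, who will review". The sentence goes on to say that this review is of the answers, for safety concerns, straight after completion. Section 9 also puts the baseline assessment and session 1 in one visit, with only the patient and the interventionist at that session. Support-team adults may be invited to sessions 2 and 3. Staff read items aloud only on need or request.

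Section 4 describes session feedback in the same way ("Because we collect feedback immediately following each session"), although that sentence is about finalising session content after phase one.

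**The concern.** A rating of a programme is open to courtesy when the rater is identifiable and the people running the programme are on the call or will see the answer. Here the raters are 12 to 18 years old and leaving partial hospitalisation, and section 5 itself treats them as open to undue influence. Live completion and prompt review are there for the suicide items. The programme ratings come under the same arrangement only because they are in the same form.

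Two features of the design make this worth attention. The trial has one arm, so an upward shift does not cancel in a comparison. And section 17 sets a bare mean against a fixed mark. If ratings are softened, a programme that falls just short could be reported as adequate, and nothing in the data would allow the effect to be separated afterwards.

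**Working it through.** **Step 1: who can see the ratings.** Setting the parts of section 9 side by side:

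- Baseline and session 1: same visit, patient and interventionist only. This is where the presence of the person delivering the programme is best supported.
- Weeks 6 and 12: live with study staff, and by Table 2 given with sessions 2 and 3, which support-team adults may attend.
- Weeks 22-24: live with study staff, with no session attached.
- Sections 9, 16 and 17 contain no independent rater, no anonymous route and no restriction that withholds the programme ratings from delivery staff.

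Section 17 does not say which administration, or what average, is compared with 3.5. Table 1 lists a youth feedback survey only at weeks 10-12 and 22-24, whereas Table 2 puts the ratings in all four surveys. On either reading the ratings are given live with staff after baseline, and at least one administration coincides with a session.

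**Step 2: what a shift would do.** The plan gives no figure to reproduce, because 3.5 is a fixed rule without a derivation. Inputs:

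- Mark 3.5 (section 17).
- n = 50 youths expected to give follow-up data, of 65 enrolled (section 5).
- Rating SD 0.9, true mean μ and courtesy shift b: all assumed, since the documents give none of them.

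Standard error = 0.9/√50 = 0.127.

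P(observed mean > 3.5) = 1 − Φ((3.5 − μ − b)/0.127)

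For example, with μ = 3.3 and b = 0, (3.5 − 3.3)/0.127 = 1.57, which gives 0.058.

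| True mean μ | b = 0 | b = 0.2 | b = 0.3 | b = 0.4 |
|---|---|---|---|---|
| 3.0 | <0.001 | 0.009 | 0.058 | 0.216 |
| 3.3 | 0.058 | 0.50 | 0.784 | 0.942 |
| 3.4 | 0.216 | 0.784 | 0.942 | 0.991 |
| 3.8 | 0.991 | >0.999 | >0.999 | >0.999 |

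**Step 3: sensitivity.** With μ = 3.4 and b = 0.2, the chance of passing runs from 0.72 (SD 1.2) to 0.81 (SD 0.8) at n = 50, and from 0.75 to 0.84 at n = 65. The choice of SD and n therefore matters little; the distance of the true mean from 3.5 matters a great deal. If all four administrations were averaged and only the three session-linked ones were affected, the shift in the mean would be 3/4 of b, so b = 0.4 would act as 0.3.

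**The case against.** The case against is substantial, and several parts of it stand.

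- **Who the audience is.** A reader might infer that the person who delivers the programme watches the youth rate it. The documents do not say so. Assessments are run by study staff and sessions by an interventionist, and the two roles are neither equated nor separated. The inference is firmest at session 1, but section 4 places baseline before the intervention starts, so the youth may have seen little of the programme by then.
- **What the youth knows.** A reader might also infer that youths know their programme ratings will be read at once. No section says they are told this. Section 8 has them told about safety evaluation only. The format is self-report, and the stated purpose of the review is safety.
- **Phase one.** It would go too far to say that these ratings decide what is changed. Section 4 names text response rates and interviews as the inputs to refinement. Section 2 gives rating scales a role alongside interviews.
- **Other evidence.** Text response rates are behavioural, and parents and support adults give their own ratings. The 3.5 mark is descriptive, with no go/no-go decision attached. This limits the consequence, but neither source enters the patient mean that section 17 compares with 3.5.
- **Size.** SD, true mean and shift are all assumed, and true means of 3.3 and 3.4 lie where a small shift has most effect.
- **Risks of a remedy.** Moving free text out of immediate review could delay the reading of a risk disclosure. A link opened after the call could be skipped by dissatisfied youths, which would bias the mean upwards again. Both points are sound and limit what should be changed.

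The gap in the plan remains: the ratings are identifiable, are collected under staff-attended conditions, and are not shielded from delivery staff.

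**Conclusion.** The point holds as a weakness in how the ratings are collected. It does not show that they will be inflated, nor that the 3.5 mark will be met wrongly; the documents give no basis for either. What they do show is that nothing prevents a courtesy effect from entering the only Aim 1 mean that has a threshold, and that no comparator would absorb it.

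On the assumed SD of 0.9 and n = 50, a shift of 0.2 to 0.4 points decides the result only when the true mean is slightly below the mark. At 3.3 the chance of passing goes from 6% to between 50% and 94%. At 3.0 it is about 1% with a shift of 0.2 and 22% even with 0.4. At 3.8 the programme passes about 99% of the time with no shift at all. This is a cheap improvement to make before data are collected, not a flaw that undermines the trial.

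**What to change.** Put only the numeric acceptability ratings in a separate REDCap form. The youth completes it privately within the scheduled assessment time, with staff neither viewing nor reading the items unless the youth asks. Close the form to that youth's interventionist until the youth has finished the study, tell the youth so, and compute the section 17 mean from it. Section 8 describes REDCap as able to "grant and control varying levels of access to data collection instruments and data", so the restriction needs no new system.

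Leave the open-ended feedback and the mood and suicide items in the survey that staff review immediately, as the plan now has it. The staff-administered interview is unchanged; it consists of open-ended questions and does not feed the 3.5 mean.

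Cost: one extra form with restricted user rights, a short addition to section 9, and possibly a few missing ratings. Report the completion rate beside the mean so that selective non-response can be seen.

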5. SUBJECT POPULATION

Number of Subjects: This study includes three sets of subjects, including (1) youth patients, (2) parents, and (3) their respective adult support team members. The subject population is the same for both phases one and two.

• Youth patients: We will enroll approximately n = 60-70 total adolescent patients in the Child and Adolescent Partial Hospitalization Service (CAPHS). The first n = 5-10 of these will be used to refine and optimize the feasibility and acceptability of YST+YM. All

Page 4 of 64 Version Date: 12/13/21 subjects will be used to evaluate target engagement. Based on consultation with CAPHS clinical director, [name] (LMSW-R), greater than 80% of patients are expected to be eligible for participation. Of eligible patients, roughly 50% are estimated to enroll in the study. Again based on consultation with [name], 75% of the initially enrolled patients are expected to complete the study. Thus, we will screen approximately 165 patients to identify 130 eligible subjects, of which 65 are expected to enroll. Given low attrition for comparable clinical programs in CAPHS (i.e., a year of pilot implementation of traditional YST in that clinic), we conservatively estimate a 25% attrition rate. Attrition will be handled with an intent-to-treat design. Given these considerations, we anticipate n = 50 subjects will provide follow-up data, providing a sufficient sample size to detect a signal for intervention target engagement.

- Parents / legal guardians: We will invite one parent / legal guardian per enrolled youth to provide feedback on the intervention, proxy-ratings of the youth's emotional well-being, as well as self-report of their own well-being. Based on consultation with clinic staff who regularly interact with this population, recruitment and retention rates for parents are expected to be roughly 80% per youth who completes the study. Thus, for the roughly n = 50 youth subjects who provide full follow-up data, we expect roughly n = 40 parents / guardians to complete all measures. This is a sample size sufficient to refine the intervention with informal feedback and to further evaluate target engagement as assessed by proxy-report.
- Adult support team members: Each adolescent patient will be encouraged to nominate n = 3-4 adults they already know and would like to serve on their support team. Because n = 65 adolescent patients are expected to enroll, this means we will screen n = 195 260 adults. Prior consultation with CAPHS clinic director [name] suggests for every 3-4 adults who are nominated, roughly 2-3 can be expected to enroll. Once enrolled, [name] indicated retention of these adults is typically greater than 90%. With these benchmarks, we thus expect n = 130 195 supportive adults to enroll in the study and roughly n = 115 175 to complete the study in its entirety.

Age of Subjects. Adolescent patient subjects must be between the ages of 12 and 18 at the time of enrollment. Adult subjects will all be over the age of 21.

Gender, Age, Racial, and Ethnic Origin of Subjects: Youth subjects will all be recruited from the Child and Adolescent Partial Hospitalization Service (CAPHS). Their demographic characteristics are thus expected to reflect the demographics of Monroe County, NY, from which CAPHS draws its patients. Adult subjects are most often members of the families and communities in which the youth subjects reside. For this reason, we expect adults to have similar demographic characteristics to the youth subjects from Monroe County, NY. Regarding race, based on US Census data from 2010-2019, the distribution of race in Monroe, NY is as follows: 76.8% White, 16.2% Black, 0.4% American Indian, 3.7% Asian, 0.1% Hawaiian, Two or More Races, 2.7% Mixed. Regarding ethnicity, 9.2% of this population is Hispanic or Latino. We will seek a similar racial and ethnic distribution in this study. The proposed study will be inclusive of all genders and we will seek to recruit an equal number of male and female subjects.

Vulnerable Subjects: The proposed study involves minors with recent suicide-related concerns. Additional protections against risks and coercion are documented below since minors are more "likely to be vulnerable to coercion or undue influence". (45 CFR 46.111(b)) Due to the vulnerable nature of the population we have strictly adhered to guidance provided in the Code of Federal Regulations (45 CFR 46 Subpart D) and specific IRB requirements for subject safety, permission and assent. These additional protections are described in the Risk/Benefit section of the protocol.

